6.1.1 Supporting documentation

This study requires supporting documentation for:

- 1) Eligibility, which includes the pathology report (including node positivity or tumor size >2.0 cm and node negative) with histologic documentation of pathologic staging, date of diagnosis and ER, PR, HER2 status (see [Section 3.2.1](#)).
- 2) Disease recurrence.
- 3) New invasive primary.

These pathology reports and any additional supporting documentation must be uploaded into RAVE at the time of Registration/Randomization and at the time of diagnosis of disease recurrence or new primary.

6.1.2 Data Quality Portal

The Data Quality Portal (DQP) provides a central location for site staff to manage unanswered queries and form delinquencies, monitor data quality and timeliness, generate reports, and review metrics.

The DQP is located on the CTSU members' website under Data Management. The Rave Home section displays a table providing summary counts of Total Delinquencies and Total Queries. DQP Queries, DQP Delinquent Forms and the DQP Reports modules are available to access details and reports of unanswered queries, delinquent forms, and timeliness reports. Review the DQP modules on a regular basis to manage specified queries and delinquent forms.

The DQP is accessible by site staff that are rostered to a site and have access to the CTSU website. Staff that have Rave study access can access the Rave study data using a direct link on the DQP.

To learn more about DQP use and access, click on the Help icon displayed on the Rave Home, DQP Queries, and DQP Delinquent Forms modules.

Note: Some Rave protocols may not have delinquent form details or reports specified on the DQP. A protocol must have the Calendar functionality implemented in Rave by the Lead Protocol Organization for delinquent form details and reports to be available on the DQP. Site staff should contact the LPO Data Manager for their protocol regarding questions about Rave Calendaring functionality.

6.2 Lifestyle Measures of Inflammation

Measures	Baseline (After agreement to participate, prior to drug start date)	At the end of 24 months of study treatment ¹
Modified Parffenbarger Questionnaire	X	X
Sleep Quality Index (PSQI)	X	X
Center for Epidemiologic Studies-Depression Scale (CES-D)	X	X
Perceived Stress Scale (PSS)	X	X
Brief Pain Index	X	X

1. Patients who discontinue study treatment before 24 months will be asked to complete the measure at the concurrent 24-month study visit.

6.3 Specimen Collection and Submission

All participating institutions must ask patients for their consent to participate in the collection of specimens planned for A011502 future analysis, although patient participation is optional. For patients who consent to A011502 biospecimen banking (consent question #1) tissue, blood, and urine will be collected at the following time points for these studies. Sites are required to provide their own materials for biospecimen collection (blood vacutainer tubes and urine specimen containers) and shipping (IATA-compatible biospecimen shipping boxes with cold packs, where necessary.

	After consent signed, prior to treatment start	At the end of 24 Months of study treatment ¹	Storage/ Shipping conditions	Submit to:
Tissue				
1 Paraffin block from resection for patients undergoing upfront surgery * OR 1 Paraffin block for patients with residual disease after neoadjuvant chemotherapy* OR 1 Paraffin block from initial diagnostic biopsy for patients who under-went neoadjuvant chemotherapy with complete or near complete pathologic response*	X		Ambient/ship overnight	WUSTL
Blood				
Whole blood				
EDTA tube Whole blood*	One 10 mL K2 or K3 EDTA lavender top anticoagulant vacutainer tube	One 10 mL K2 or K3 EDTA lavender top anticoagulant vacutainer tube	Cool pack/ship over night	WUSTL

* See Sections 6.3.4 and 6.3.5 ¹ Patients who discontinue study treatment will be asked to provide the whole blood and spot urine samples at the concurrent 24-month visit.

Urine				
Spot Urine			Cool pack/ship over night	
Spot Urine*	Two 15 ml falcon tubes with 10ml of urine per tube	Two 15 ml falcon tubes with 10ml of urine per tube		WUSTL

6.3.1 Specimen submission using the Alliance Biospecimen Management System

USE OF THE ALLIANCE BIOSPECIMEN MANAGEMENT SYSTEM (BioMS) IS MANDATORY AND ALL SPECIMENS MUST BE LOGGED AND SHIPPED VIA THIS SYSTEM.

BioMS is a web-based system for logging and tracking all biospecimens collected on Alliance trials. Authorized individuals may access BioMS at the following URL:

[REDACTED] using most standard web browsers (Safari, Firefox, Internet Explorer). For information on using the BioMS system, please refer to the 'Help' links on the BioMS webpage to access the on-line user manual, FAQs, and training videos. To report technical problems, such as login issues or application errors, please contact: [REDACTED] For assistance in using the application or questions or problems related to specific specimen logging, please contact: [REDACTED]

After logging collected specimens in BioMS, the system will create a shipping manifest. This shipping manifest must be printed and placed in the shipment container with the specimens.

All blood and urine specimens must be labeled with the protocol number (A011502), Alliance patient number, patient's initials, date and type of specimen collected (e.g., urine, whole blood).

Any surgical pathology tumor block or unstained slides submitted MUST be accompanied by a corresponding de-identified surgical pathology report labeled with the protocol number (A011502) and Alliance patient number.

[figure not shown]
A copy of the Shipment Packing Slip produced by BioMS must be printed and placed in the shipment with the specimens.

Instructions for the collection of samples are included below. Please be sure to use a method of shipping that is secure and traceable. Extreme heat precautions should be taken when necessary.

Ship specimens on Monday through Thursday only. Shipping by overnight service to assure receipt is encouraged. Do not ship specimens on Fridays or Saturdays.

All specimens should be sent to the following address:

Alliance Biorepository at Washington University

6.3.2 Collection of tissue, blood and urine

For patients who consent to participate in the optional specimen collection and banking, tumor blocks will be banked for future analyses and potential correlative studies.

6.3.3 Collection of paraffin blocks

Paraffin blocks of primary tissue obtained from archival tumor specimens should be sent to the Alliance Biorepository at Washington University (WUSTL) within 30 days of patient registration/randomization.

The Alliance has instituted special considerations for the small percentage of hospitals whose policy prohibits long-term storage of blocks, and the smaller percentage of hospitals whose policies prohibit release of any block. If, due to institutional policy, a block cannot be sent, three unstained slides, cut at 4-6 micron in thickness and mounted on charged glass slides will be requested. Slides should be labeled as follows: Each slide must be labeled with the specimen surgical pathology number and block number either via your institutions standard method for labeling clinical slides or using a permanent marker. Please DO NOT use sticky labels. The labeling of study number, patient ID, patient Initials, sample type, and collection time is no longer required on slides.

The goal of the Alliance Biorepository at Washington University is to provide investigators with quality histology sections for their research while maintaining the integrity of the tissue. For this reason, it is preferred that the Alliance Biorepository at Washington University bank the block until the study investigator requests thin sections. Please contact the Alliance Biorepository at Washington University if additional assurances with your hospital pathology department are required.

Be certain to include a de-identified surgical pathology report, which includes the surgical pathology case number and tissue block identifier that matches the submitted block or labeled slides.

For patients who are simultaneously enrolled to another Alliance trial (e.g. A011401) at the same time as this study, and there is insufficient tissue available to be submitted separately for both studies, please prioritize the tissue for the current A011502 study and ship the tissue to the Alliance Biorepository at Washington University in St. Louis. Please select “not collected” in BioMS for the other trial to which the patient may be enrolled (e.g. A011401) for tissue submission, select “other” as the reason for not collecting the specimen, and note in the comments area that tissue has been submitted to for A011502 study, along with the A011502 participant ID.

6.3.4 Blood sample submission

Collect 10 mL of venous blood in one K2 or K3 EDTA lavender top anticoagulant vacutainer tube. The tubes should be inverted approximately 8-10 times to mix the EDTA. Refrigerate sample until shipping. The sample should be placed in a biohazard bag and shipped according to IATA guidelines the same day as the blood is drawn on a cold pack by overnight courier service to the Alliance Biorepository at Washington University. Blood samples will be processed into plasma and buffy coat for long term storage by the Alliance Biorepository at Washington University (WUSTL).

6.3.5 Urine sample submission

Spot urine collection should follow institutional standard procedures. For each collection, 20 mls of urine should be transferred into two 15 ml falcon tubes (10 ml per tube) or any equivalent collection container, and be shipped overnight with a cold pack to the Alliance Biorepository at Washington University. Ensure that the collection containers are sealed, fluid-tight, and that lids will not become insecure during transit.

Urine samples will be stored as 2 ml aliquots in LN2 vapor until retrieved for correlative science assays.

Label blood and urine samples with the following identification:

- 1) Specimen procurement date and time
- 2) Alliance patient number
- 3) Alliance study number (A011502)
- 4) Specimen type: Whole blood; spot urine.

7.0 TREATMENT PLAN/INTERVENTION

Protocol treatment is to begin \leq 28 days of registration/randomization. This is a double blinded, placebo controlled trial. Patients will be randomized with equal probability to receive treatment with aspirin or placebo.

7.1 Study Treatment

Agent	Dose	Route	Day
Aspirin/Placebo	One 300 mg tablet	Oral	Daily x 5 years

After registration, blinded, patient-specific supplies of aspirin/placebo are to be ordered by the site by completing the drug order form (see [Section 10.0](#)).

Patients should be given a six-month supply of study drug in order to correspond with study visit schedule in [Section 5.0](#).

7.2 Adherence

Since patients will take oral medications at home without direct supervision, we will monitor drug compliance until the discontinuation of aspirin/placebo using A011502 Study Medication Logs (Appendix II). At study entry the patient will receive the Medication Log and be instructed on how to take the medication and how to use the Log. The patient will bring the Log to each visit where it will be reviewed with a member of the study team. The patient will then be given a new Log to record study medication until the next visit. If a patient cites reasons other than drug side effects for not taking the required medication, the reasons for missed doses will be reviewed and the importance of taking all doses on schedule will be reinforced. The study team member will document the patient-reported dosage in the patient's medical record and determine if the patient was compliant for that study period and document compliance on the appropriate study forms. Compliance is defined as patient self-report of taking 80% of study tablets.

Non-protocol use of aspirin and NSAIDs will also be monitored every 6 months along with study drug compliance.

7.3 Disease Recurrence and New Invasive Disease

Upon disease recurrence or new invasive second primary, except for basal or squamous cell carcinoma of the skin, protocol treatment will be discontinued and treatment will then be at the discretion of the treating physician.

8.0 DOSE AND TREATMENT MODIFICATIONS, UNBLINDING

8.1 Ancillary Therapy, Concomitant Medications, and Supportive Care

8.1.1 Patients should receive full supportive care while on this study. This includes blood product support, antibiotic treatment, and treatment of other newly diagnosed or concurrent medical conditions. All blood products and concomitant medications such as antidiarrheals, analgesics, and/or antiemetics received from the first day of study treatment administration until 30 days after the final dose must be recorded in the medical records.

8.1.2 Antiemetics may be used at the discretion of the attending physician. Analgesics and/or antiemetics received from the first day of study treatment administration until 30 days after the final dose must be recorded in the medical records.

8.1.3 Proton pump inhibitors (PPIs) may be used at the discretion of the treating study physician.

*For patients who require a PPI, US sites only may order the PPI through the Alliance while funding is available. Instructions for ordering the PPI are located on the A011502 study pages on the Alliance and CTSU websites.

8.1.4 Non-protocol use of aspirin and/or NSAIDs is discouraged. However, non-protocol use of these medications will not result in removal from study, but must be noted on

the appropriate study form. Instead, use of acetaminophen for treatment of aches, pains, and fevers is encouraged.

8.1.5 Concomitant endocrine therapy

Patients with hormone receptor (ER and/or PR) positive disease should receive a minimum of 5 years of standard endocrine therapy (experimental agents/regimens are not permitted). Endocrine therapy should begin following completion of neoadjuvant chemotherapy and surgery, either before, during or after radiation therapy at discretion of oncologist. Selection of the agents is at the treating physician's discretion.

8.1.6 Study drug should be held while on lovenox or other daily anticoagulation medications.

8.1.7 Co-enrollment in other clinical trials

Patients are able to co-enroll on these studies only if they have completed radiation, chemotherapy or surgery and meet all other A011502 eligibility criteria. For the studies listed below, you do not need to ask for a separate confirmation from the A011502 Study Chair. However, for those studies that are NOT listed, please contact the study Protocol Coordinator at the email or phone number listed on the cover page of this protocol.

Trials for which co-enrollment is allowed:

Trials involving everolimus, palbociclib, PARP inhibitors, such as:

AFT-05 PALLAS: PALbociclib CoLLaborative Adjuvant Study: A Randomized Phase III Trial of Palbociclib With Standard Adjuvant Endocrine Therapy Versus Standard Adjuvant Endocrine Therapy Alone for Hormone Receptor Positive (HR+) / Human Epidermal Growth Factor Receptor 2 (HER2)-Negative Early Breast Cancer (PALLAS).

Alliance A011401: Randomized Phase III Trial of Evaluating the Role of Weight Loss in Adjuvant Treatment of Overweight and Obese Women with Early Breast Cancer.

SWOG S1207: Phase III Randomized, Placebo-Controlled Clinical Trial Evaluating the Use of Adjuvant Endocrine Therapy +/- One Year of Everolimus in Patients with High-Risk, Hormone Receptor-Positive and HER2/Neu Negative Breast Cancer. e³ Breast Cancer Study-Evaluating Everolimus with Endocrine Therapy.

Trials for which co-enrollment is allowed after completion of radiation and chemotherapy:

Per Section 3.2.3, all adjuvant treatment with chemotherapy and/or radiation must be completed at least 30 days prior to registration. A patient may enroll on A011502 after they have completed radiation therapy and/or chemotherapy on the following trials provided that they meet all other eligibility criteria.

Surgery trials:

ALLIANCE A011202: A Randomized Phase III Trial Comparing Axillary Lymph Node Dissection to Axillary Radiation in Breast Cancer Patients (cT1-3 N1) Who Have Positive Sentinel Lymph Node Disease After Neoadjuvant Chemotherapy.

Radiation trials:

NRG B51: A Randomized Phase III Clinical Trial Evaluating Post-Mastectomy Chest wall and Regional Nodal XRT and Post-Lumpectomy Regional Nodal XRT in Patients with Positive Axillary Nodes Before Neoadjuvant Chemotherapy Who Convert to Pathologically Negative Axillary Nodes After Neoadjuvant Chemotherapy.

Chemotherapy Trials:

ECOG EA1131: A Randomized Phase III Post-Operative Trial of Platinum Based Chemotherapy vs. Observation in Patients with Residual Triple-Negative Basal-Like Breast Cancer Following Neoadjuvant Chemotherapy after the completion of carboplatin or capecitabine.

NRG BR-003: A Randomized Phase III Trial of Adjuvant Therapy Comparing Doxorubicin Plus Cyclophosphamide Followed by Weekly Paclitaxel with or Without Carboplatin for Node-Positive or High-Risk Node-Negative Triple-Negative Invasive Breast Cancer

8.2 Dose Modifications

8.2.1 Dose Levels

Dose Level	Drug Name	Dose
0*	Aspirin	300 mg
-1	Aspirin	100 mg

*Dose level 0 refers to the starting dose.

If dose reduction below level -1 is required, permanently discontinue protocol therapy.

8.2.2 Hematologic Adverse Events

8.2.2.1 Grade 1 bleeding

For grade 1 bleeding, one level dose reduction will be allowed at physician discretion.

8.2.2.2 Grade 2 bleeding

For grade 2 bleeding, one level dose reduction will be required.

For recurrent Grade 2 bleeding after dose reduction, discontinue protocol therapy.

8.2.2.3 Grade 3 and 4 gastrointestinal bleeding or active gastrointestinal ulceration

Grade 3 and 4 GI bleeding will require that the patient be permanently removed from protocol treatment.

8.2.2.4 Other grade 1 and 2 non-bleeding related gastrointestinal toxicity

A proton pump inhibitor will be prescribed for the patient at the discretion of the treating physician. Alternatively, at the discretion of the treating physician, one level dose reduction may be performed.

8.2.3 Cardiovascular toxicities and thrombotic events**8.2.3.1 For grade 3 or 4 cardiac ischemia/infarction or thrombosis: Permanently discontinue protocol therapy.****8.2.3.2 For grade 1 toxicity, no change in study drug dosage is required.**

For grade 2 toxicity, reduce to dose level -1, at physician discretion. If dose is reduced, patients should continue at this dose for the duration of study treatment.

8.2.4 Intracranial hemorrhage: Permanently discontinue protocol therapy for any grade intracranial bleeding.**8.2.5 Macular Degeneration: Permanently discontinue protocol therapy for any grade macular degeneration considered related to aspirin/placebo.****8.2.6 Tinnitus or hearing loss: Permanently discontinue protocol therapy for any grade considered related to aspirin/placebo.****8.2.7 Dermatologic toxicities: Permanently discontinue protocol therapy for Stevens-Johnson syndrome or toxic epidermal necrolysis.****8.2.8 Other non-hematologic toxicities attributed to aspirin/placebo**

For other grade 3 or 4 non-hematologic toxicities considered related to aspirin/placebo, interrupt aspirin/placebo, for a maximum of 28 days until toxicity improves to \leq grade 2, then resume aspirin/placebo, with one dose reduction.

For recurrence of the same grade 3 or 4 non-hematologic toxicity considered related to aspirin/placebo, or if toxicity does not improve after 28 days, permanently discontinue aspirin/placebo.

For persistent grade 2 non-hematologic toxicity considered related to aspirin/placebo that the patient finds unacceptable, interrupt aspirin/placebo for a maximum of 28 days until toxicity improves to \leq grade 1, then resume aspirin/placebo at the previous dose.

For recurrence of unacceptable grade 2 non-hematologic toxicity considered related to aspirin/placebo, or if grade 2 toxicity does not improve after 28 days, permanently discontinue aspirin/placebo.

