9.1 Routine Adverse Event Reporting

Adverse event data collection and reporting, which are required as part of every clinical trial are done to ensure the safety of patients enrolled in the studies as well as those who will enroll in future studies using similar agents. Adverse events are reported in a routine manner at scheduled times according to the study calendar in Section 5.0. For this trial, the Adverse Events: Solicited form is used for routine AE reporting in Rave.

Solicited Adverse Events: The following adverse events are considered "expected" and their presence/absence should be solicited, and severity graded, at baseline and for each cycle of treatment.

• CTCAE v 4.03 Term	• CTCAE v4.0 Organ Class (SOC)
• Gastrointestinal bleeding	• Gastrointestinal disorders
• Intracranial hemorrhage	• Nervous system disorders
• Epistaxis	• Respiratory, thoracic and mediastinal disorders
• Hematuria	• Renal and urinary disorders
• Dyspepsia	• Gastrointestinal disorders
• Gastritis	• Gastrointestinal disorders
• Bruising	• Injury, poisoning and procedural complications

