9.2 CTCAE Routine Reporting Requirements

In addition to the solicited adverse events listed in [Section 9.1](#), the following table outlines the combinations of time points, grades and attributions of AEs that require routine reporting to the Alliance Statistics and Data Center. Questions about routine reporting should be directed to the Data Manager.

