***Combinations of CTCAE Grade & Attribution Required for Routine AE Data Submission on Case Report Forms (CRFs)**

Attribution	Grade 1	Grade 2	Grade 3	Grade 4	Grade 5
Unrelated			a	a	a
Unlikely			a	a	a
Possible		a	a, b	a, b	a, b
Probable		a	a, b	a, b	a, b
Definite		a	a, b	a, b	a, b

- a) Adverse Events: Other CRF - Applies to AEs occurring between registration and within 30 days of the patient's last treatment date, or as part of the Clinical Follow-Up Phase.
- b) Adverse Events: Late CRF - Applies to AEs occurring greater than 30 days after the patient's last treatment date.

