Methotrexate: Salicylate can inhibit renal clearance of methotrexate, leading to bone marrow toxicity, especially in the elderly or renally impaired.

Nonsteroidal Anti-Inflammatory Drugs (NSAIDs): Concomitant administration of NSAIDs and aspirin may lead to increased bleeding or decreased renal function. Avoid concurrent use.

Oral Hypoglycemics: Moderate aspirin doses may increase the effectiveness of oral hypoglycemic agents causing hypoglycemia.

Uricosuric Agents: (Probenecid and Sulfinpyrazone): Salicylates antagonize the uricosuric action of uricosuric agents.

Pharmacokinetics

Absorption: Immediate, rapid and completely absorbed from gastrointestinal tract.

Distribution: Widely distributed to all tissues and fluids in the body including the central nervous system (CNS) and breast milk and fetal tissues. The highest concentrations are found in the plasma, liver, renal cortex, heart and lungs. The protein binding of salicylate is concentration-dependent, i.e. non-linear.

Metabolism: Hydrolyzed to salicylate (active by esterases in GI mucosa, red blood cells, synovial fluid and blood; metabolism of salicylate occurs primarily by hepatic conjugation; metabolic pathways are saturable).

Excretion: Urine (75% as salicyluric acid, 10% as salicylic acid).

T1/2: Parent drug 15 to 20 minutes; Salicylates 3 hours.

Adverse Events

Cardiovascular: Cardiac arrhythmia, edema, hypotension, tachycardia.

Central Nervous System: Agitation, cerebral edema, coma, confusion, dizziness, fatigue, headache, hyperthermia, insomnia, lethargy, nervousness, Reye's syndrome.

Dermatologic: Skin rash, urticarial.

Endocrine & Metabolic: Acidosis, dehydration, hyperglycemia, hyperkalemia, hypernatremia (buffered forms), hypoglycemia (children).

Gastrointestinal: Gastrointestinal ulcer, duodenal ulcer, dyspepsia, epigastric distress, gastritis, gastrointestinal erosion, heartburn, nausea, stomach pain, vomiting.

Genitourinary: Postpartum hemorrhage, prolonged gestation, prolonged labor, proteinuria, stillborn infant.

Hematologic & Oncologic: Anemia, blood coagulation disorder, disseminated intravascular coagulation, hemolytic anemia, hemorrhage, iron deficiency anemia, prolonged prothrombin time, thrombocytopenia.

Hypersensitivity: Anaphylaxis, angioedema.

Neuromuscular & Skeletal: Acetabular bone destruction, rhabdomyolysis, weakness.

Otic: Hearing loss, tinnitus.

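### Related grade 1 tinnitus, hearing loss or macular degeneration ends treatment but is neither solicited nor reportable, so the toxicity comparison can miss it

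*Combined protocol and SAP*

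**What the plan says.** Stopping rules. Section 8.2.6: "Tinnitus or hearing loss: Permanently discontinue protocol therapy for any grade considered related to aspirin/placebo". Section 8.2.5: "Macular Degeneration: Permanently discontinue protocol therapy for any grade macular degeneration considered related to aspirin/placebo". Both apply at every grade, and both apply only when the event is judged related to study drug.

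Solicited events. Section 9.1 states: "For this trial, the Adverse Events: Solicited form is used for routine AE reporting in Rave". It lists seven terms: gastrointestinal bleeding, intracranial hemorrhage, epistaxis, hematuria, dyspepsia, gastritis and bruising. For these, "their presence/absence should be solicited, and severity graded, at baseline and for each cycle of treatment". The three events above are not listed.

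Other events. Section 9.2 adds that "the following table outlines the combinations of time points, grades and attributions of AEs that require routine reporting". In that grid, grade 1 is empty for all five attribution levels, grade 2 is required when the attribution is possible, probable or definite, and grades 3 to 5 are always required.

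Known effects. Section 10.1 lists "Otic: Hearing loss, tinnitus" among aspirin's adverse events and names age-related macular degeneration under postmarketing and case reports. The instructions that follow Section 9.3.1 count Section 10.0 events as expected.

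Analysis. Objective 2.2.2 compares toxicity between arms. Section 13.3.3 does so by event type and maximum grade, with Fisher exact tests, in patients who took at least one dose.

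**The concern.** A treatment-stopping rule and the data collection behind the safety comparison should cover the same events. Here the rule starts at grade 1, while required collection for these three events starts at grade 2. An event serious enough, under the protocol, to end treatment for good may leave no trace in the dataset from which tolerability will be judged.

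Two things are at stake. First, the count of such events can be too low in both arms. If aspirin causes more of them than placebo, the absolute difference is understated as well. Second, because the terms are not solicited, no baseline grade is required. Pre-existing tinnitus or hearing loss is then not systematically on record when the investigator has to decide whether a later complaint is related, and that decision is what triggers the stop.

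**Working it through.** The plan states no figure on this point, so there is nothing to reproduce. The check sets the provisions side by side. I read an event considered related as one attributed as possible, probable or definite; the protocol does not define this mapping.

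| Event | Ends treatment | Solicited (9.1) | Routine report required (9.2) | Reaches the 13.3.3 comparison |
|---|---|---|---|---|
| Related tinnitus, hearing loss or macular degeneration, grade 1 | Yes (8.2.5, 8.2.6) | No | No | Only if the site reports it without being required to |
| Same, grade 2 | Yes | No | Yes | Yes |
| Same, grades 3 to 5 | Yes | No | Yes | Yes |
| Intracranial hemorrhage, any grade | Yes (8.2.4) | Yes | Already on the solicited form | Yes, at every grade |

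The last row is the useful contrast. Intracranial hemorrhage is also a permanent stop at any grade, and there the protocol does match its collection to its rule. Bruising is solicited and graded from grade 1 although it is not singled out for a permanent stop in Section 8.2. The omission of the otic and macular terms therefore looks like a mismatch between sections rather than a deliberate threshold.

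Other routes that might close the gap:

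1. Expedited reporting. The Section 9.3.1 table covers serious events and does not require a report for grade 1 without hospitalization. An ordinary grade 1 tinnitus is not captured.
2. Adherence reporting. Section 13.4.1 summarizes compliance among patients on treatment at each visit, so a patient who has stopped is no longer in that denominator.
3. Reason for stopping. Section 12.1.2 names adverse events among the reasons for early discontinuation, but no analysis of reasons by arm is specified, and the forms are not in the documents.

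None of the three secures the grade 1 record in the planned analysis.

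**The case against.** The strongest reply is that the gap is narrow and may be partly filled in practice. The Section 5.0 calendar has an adverse event assessment, history and physical examination every 6 months, and an adverse event assessment at the end of treatment, so patients are asked about their health in general. The grid sets what must be reported and does not forbid a grade 1 report. An off-treatment form may record the specific cause. All of this is fair. It means one cannot say that these events will be absent from the trial's records, only that the protocol does not require them to be present.

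A reader might infer three stronger things that the documents do not support:

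- That the toxicity comparison is blind to these events altogether. It is not: related grade 2 and all grade 3 to 5 events are reportable and enter the comparison.
- That attribution hides treatment-ending grade 2 events. It does not: the stop applies only to events considered related, and related grade 2 events are exactly those that the grid requires.
- That the stop operates only if the patient happens to raise the symptom. The scheduled assessments are an enquiry, even without a checklist row for these terms.

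It is also true that the point touches one secondary objective and leaves iDFS, its test and the futility rule unaffected.

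**Conclusion.** The point holds for grade 1 events considered related to study drug. Following the protocol to the letter allows such an event to end treatment permanently without any required adverse event record, and the Section 13.3.3 comparison can therefore miss it. For grade 2 and above, what remains is the ordinary limitation of unsolicited reporting without a required baseline grade.

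No numerical size is claimed. The documents give neither the rate of these events nor the share that is grade 1, and any count would be an assumed rate multiplied by the arm size. The conclusion rests on the text of Sections 8.2.5, 8.2.6, 9.1 and 9.2, on reading related as at least possible, and on the absence of any other stated requirement. The case report forms could soften it if they capture the causal event at discontinuation. The consequence is limited to the safety comparison, but the remedy is cheap enough that it should be made. Whether the stopping rules themselves are right is not judged here.

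**What to change.** Three changes to data collection and analysis:

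1. Amend Sections 9.1 and 9.2 so that any adverse event, at any grade, that leads to permanent discontinuation must be recorded on the adverse event form. This alone closes the gap, and the end-of-treatment assessment already in the calendar is a natural place for it.
2. Add tinnitus and hearing impairment to the solicited form at baseline and each 6-month visit, so that a baseline grade exists. Macular degeneration may be added as a reported diagnosis if wanted. The calendar has no eye examination and none needs to be added, so that row would capture only what is already known to the patient or site.
3. Add to Section 13.3.3 a table of adverse-event discontinuations by event type and arm.

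The discontinuation rules are unchanged. The cost is a few rows on a form that is already completed at each visit, a small burden for sites, and a minor amendment. If the amendment comes after enrollment has begun, events from before it will have been collected under the present rules, and the report should say so.
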